### **DDR1 activity as a predictor of efficacy of regorafenib**

[name]., Centre de Recherche en Biologie cellulaire de Montpellier

[name]., Ph.D., ICM, IRCM, Montpellier

DDR1 is a tyrosine kinase receptor for collagens, which are major components of CRC microenvironment. DDR1 functions as a central extracellular matrix sensor to regulate cell adhesion and to promote tumor cell invasion and cancer stem cell survival in a collagen rich microenvironment (14, 15). Interestingly, the DDR1 kinase activity seems to be dispensable for several DDR1 functions reported in human cancers (16). Our group recently reported important DDR1 kinase-dependent function in CRC metastasis formation and also showed that DDR1 inhibition provided significant anti-tumor activity in this cancer (17). Actually, we showed that DDR1 pharmacological inhibition by a potent DDR1 inhibitor (i.e. nilotinib) inhibits the invasive and metastatic behavior of CRC cells through a RAS-independent mechanism. We were able to inhibit the DDR1-mediated metastatic potential of CRC cells in a liver metastasis mouse model and of patient-derived cell lines originating from metastatic tumors and circulating CRC cells. DDR1 inhibition displayed too anti-tumor activity in mice that have already developed DDR1-dependent metastatic nodules, revealing an additional important role of DDR1 activity in metastatic growth (17). Clinical relevance of our findings is further supported by showing that DDR1 expression level is an independent marker of poor prognosis in stage IV patients, and is not correlated with already described variables like tumor location, grade, number of metastatic sites, and CMS transcriptional subtypes. Besides, its relative kinase activity was dramatically increased in CRC metastatic nodules (mean > 10 fold) from a small cohort of patient with mCRC (12/20 patients), when compared to non-transformed tissue or primary tumors of the same patients. This observation is consistent with a DDR1 kinase role in liver metastatic development of CRC patients (17). We thus propose that targeting tumor signaling emanated from the

microenvironment through inhibition of DDR1 activity could be an effective strategy to treat mCRC.

Interestingly, regorafenib is also a potent inhibitor of DDR1 (as well as its M2 and M5 metabolites), with a  $K_d$  identified (0.9 nmol/L) as the lowest of all the kinases being inhibited (18). Based on our previous experience with another DDR1 inhibitor, we postulate that the antioncogenic properties of regorafenib (as opposed to its inhibitory properties against various stromal and angiogenic targets) are mainly driven by DDR1 inhibition.

**Taking avantage of the present FOLFIRINOX-R trial, we would like to:**

1. assess the baseline activity of DDR1 in colorectal samples,
2. to compare the baseline DDR1 activity to the one of patients (actually those who present some degree of tumor shrinkage) who undergo primarily unplanned hepatectomy and let liver metastases available to study,
3. to correlate baseline DDR1 activity to FOLFIRINOX-R efficacy (response rate, PFS, progression-free survival since maintenance therapy onset with regorafenib),
4. to correlate DDR1 activity on resected liver metastases to the time to recurrence.
5. To proceed to the following additional *in vitro* and *in vivo* experiments in order to strengthen the importance of DDR1 inhibition provided by regorafenib:
  - Test the capacity of regorafenib (1-10nM) to inhibit invasive properties of colorectal tumor cells induced by DDR1 overexpression in collagen matrix *in vitro*.
  - Test *in vivo* the capacity of regorafenib treatment (10mg/kg) to block metastatic development induced by DDR1 overexpression in colorectal tumor cells that were transplanted in the spleen of nude mice.

➤ **Actually, with this translational research, we aim to assess DDR1 activity as a predictor of efficacy in mCRC patients treated with a regorafenib-based therapy.**

**Expected results:** Our hypothesis is that a high DDR1 kinase activity level is associated with a shorter PFS/OS in patients with CRC, as already reported at the DDR1 transcript level and suggested on DDR1 activity from a small cohort of patients with metastatic CRC (17). Based on the metastatic function of DDR1 in CRC, the level of DDR1 activity may be a marker of its metastatic function in patient tumor samples. Regorafenib may reduce metastatic growth in “DDR1 high” CRC and a correlation is expected between high DDR1 tumor activity and tumor response to regorafenib. We also predict that, due to the high affinity of regorafenib to

DDR1, this kinase inhibitor may block all DDR1 invasive/metastatic activities in CRC experimental models described above.

### **cfDNA monitoring**

- [name]., Institut de Recherche sur le Cancer de Montpellier (IRCM)
- [name]., Ph.D., ICM, IRCM
- [name]., Ph.D., ICM, IRCM

Our group developed a Q-PCR based-method (Intplex) which is a mutation targeted test that enables rapid, highly sensitive, cost effective and repetitive analysis (19, 20). We carried out the first clinical validation of cfDNA analysis in oncology, i.e. in colorectal cancer (21) using this test. Thus, we performed a blinded prospective multicenter study to compare *KRAS* and *BRAF* mutation status data obtained from the analysis of tumor tissue by routine gold-standard methods and of plasma DNA from mCRC patients before initiation of anti-EGFR therapy. The mutation status was determined by both methods from 106 patient samples. cfDNA analysis showed 100% specificity and sensitivity for the *BRAF V600E* mutation. For the seven tested *KRAS* point mutations, the method exhibited 98% specificity and 92% sensitivity with a concordance value of 96%. Mutation load, expressed as the proportion of mutant alleles in cfDNA, was highly variable (0.5–64.1%, median 10.5%) among mutated samples. CfDNA was detected in 100% of patients with mCRC. This study carried out under the most stringent criteria for determining performance of a diagnostic test (STARD criteria) shows that liquid biopsy through cfDNA analysis could advantageously replace tumor-section analysis and expand the scope of personalized medicine for patients with cancer (21, 22). Considering the results we accumulated, works from other groups, clinical use of cfDNA analysis in general or in the context of the selection of mCRC patients toward targeted therapy is warranted in the coming years.

In this context, we are currently investigating, within the PANIRINOX trial (sponsor: UNICANCER), the clinical efficacy reached with an intensified regimen combining FOLFIRINOX plus panitumumab in mCRC patients with *RAS* wild-type status determined by cfDNA analysis in comparison with the standard treatment of FOLFOX6 plus panitumumab (23).

- **Considering this active screening of mCRC patients with *RAS* wild-type cfDNA, we have an obvious opportunity to select for research purpose, mCRC patients with *RAS*-mutant cfDNA.**

Because cfDNA analysis has the capacity to reflect tumor load, it has also been used to monitor the efficacy of response of mCRC patients to treatment, in a few retrospective series with a small number of patients (24-26)

- **Actually, with this translational research, we aim to better understand the changes of RAS-mutant cfDNA concentration along a regorafenib-based therapy**

## 2. Study objectives and Endpoints

### 2.1 Objectives

#### 2.1.1 Primary objectives

##### Phase I:

- To determine the maximum tolerated dose (MTD) and the recommended phase II dose (RP2D), based on the Dose Limiting Toxicities (DLT) of the combination evaluated during the three first cycles following initiation of therapy (observational period)
- To evaluate the safety profile of the combination.

**Phase II:** To evaluate the efficacy (48-week disease-control rate) of study combination

#### 2.1.2 Secondary objective

These apply to phase II part of the project.

They include the following evaluations:

- Safety of combination (NCI-CTC v5, neurotoxicity being also evaluated with the Levi's scale – appendix 2)
- Overall response rate and disease control rate according to RECIST 1.1
- Duration of response in patients who were not operated on for their metastases
- Study of variations in the concentration of Ras-mutant cfDNA during treatment,
- 8-weeks response rate according to RECIST 1.1
- Deepness of response

- Resectability (R0,R1) and unresectability rates (including R2) among patients with liver-only metastases
- Progression-free survival
- Progression-free survival since maintenance therapy onset with regorafenib
- Overall survival

As translational studies:

- Impact of DDR1 kinase activity on response, PFS and progression-free survival since maintenance therapy onset with regorafenib, and study of the variation of DDR1 activity in patients whom liver mets are deemed resectable.
- Select a population of mCRC with *RAS*-mutant cfDNA (already done in the PANIRINOX trial)
- Describe the distribution of baseline genotype(s) of *RAS*-mutant cfDNA
- Monitor the *RAS* mutant-allele concentration along FOLFIRINOX-R therapy
- Correlate the baseline *RAS* mutant-allele concentration and the deepness of decrease of this concentration during FOLFIRINOX-R with PFS and with the progression-free survival since maintenance therapy onset with regorafenib.

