### 4.2 Inclusion criteria

#### Eligibility criteria for prescreening

The following criteria must be met at the time of prescreening:

1. Written informed consent for prescreening.
2. Prescreening of patients will be performed at the investigators' discretion up to a maximum of 21 days prior to full study screening. Investigators should ensure all patients will be eligible in terms of disease status within this timeframe.
3. Age  $\geq 18$  years.
4. Histological documentation of adenocarcinoma of the colon or rectum.
5. Synchronous or metachronous metastatic colorectal cancer not amenable to surgical resection with curative intent.
6. No prior therapy for metastatic disease.
7. Eastern Cooperative Oncology Group (ECOG) performance status  $\leq 1$ .
8. Life expectancy of at least 3 months.

Besides these basic criteria, any criterion as outlined below under inclusion eligibility criteria for full study and exclusion criteria, already known to prohibit the patient's participation in the study should be considered. No study-related procedures will be performed that are not covered by the prescreening informed consent form.

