Including skin assessment for toxicities

Pre-menopausal women of childbearing potential only

12-lead ECG will be performed before and after the administration of Oxaliplatin during the three first cycles (Phase I and II) beyond cycle 3, ECG will be performed before administration of oxaliplatin

Includes: albumin, creatinine, creatinine clearance calculated according MDRD, lipase, glucose, TSH (every 6 weeks of CXD1), , total protein and uric acid

Liver function tests will be performed weekly during the three first cycles of treatment

Not required at day 1 of cycle 1 if those were completed within 7 days

Dipstick assessment with pH, protein, glucose, bilirubin, ketones, blood cells and leucocytes

CT scan of the abdomen, pelvis and chest or if the patient is allergic to iodine contrast agents, hepatic MRI and CT scan of the pelvis and chest without injection; RECIST criteria version 1.1

CT-Scans will be performed every 8 weeks

If the last radiological tumor assessment > 1 month

CT-Scan of safety follow-up will be performed if only it weren't done at the EOT visit

Period for DLT assessment is the three first cycles (only Phase I)

Height only at screening

Blood pressure will be monitored every other week during the first 3 cycles of treatment

Continuously from screening until FU visit, 30 days after last administration of study drug

A treatment diary will be handed over to patient on cycle 1 day 1

Three EDTA tubes will be collected at baseline, every 8 weeks during treatment and at the end of treatment

Paraffin-embedded human solid tissue blocks will be sent off at room temperature at the end of the enrollments

Only for unstabilized adverse events since the end of treatment

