## 6.4 Treatment duration

12 cycles have to be delivered consecutively or not.

Indeed, treatment can be temporarily stopped to perform surgical resection or regional procedures (radiofrequency, cryoablation, radiation therapy) if the disease become accessible to them but if it happens, before the end of the 12 planned cycles, the treatment

has to be resumed within 4 to 8 weeks after the loco-regional procedure has been completed in order to reach a total number of 12 cycles delivered.

If a surgery or a regional procedure is considered, we recommend respecting a time period of 4 weeks between the last chemotherapy and the procedure.

After 12 cycles, patients whose metastases are not progressing and are still unresectable will receive regorafenib (experimental regimen and at the same dose) until progression or toxicity.

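### Duration of response is planned only in patients not operated on, a group fixed after response begins, so it tends to understate the duration for responders as a whole

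*Combined protocol and SAP*

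**What the plan says.** The secondary objectives, in the synopsis and in section 2.1.2, include "Duration of response in patients who were not operated on for their metastases". No other text specifies duration of response. It is absent from the secondary endpoints (2.2.2), the assessment criteria (9.4) and the statistical methods (10.3), where Kaplan-Meier is named for PFS and OS only. The protocol gives it no start, end event, denominator or censoring rule, and plans no estimate in all responders. Section 10.3 leaves further detail to an analysis plan to be written before the database is closed.

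Three other places bear on who is operated on:

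- Section 4.2, prescreening criteria, requires "Synchronous or metachronous metastatic colorectal cancer not amenable to surgical resection with curative intent".
- Section 6.4 says that "treatment can be temporarily stopped to perform surgical resection or regional procedures (radiofrequency, cryoablation, radiation therapy) if the disease become accessible to them", and on timing that "we recommend respecting a time period of 4 weeks between the last chemotherapy and the procedure".
- Section 1, on the DDR1 study, describes the patients expected to provide resected liver tissue as "those who present some degree of tumor shrinkage) who undergo primarily unplanned hepatectomy and let liver metastases available to study".

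**The concern.** Patients enter unresectable, so being operated on is always a post-baseline event, and for a responder operated on during response it comes after response onset. A responder who progresses early will normally not reach surgery and stays in the analysis. A responder who remains controlled until surgery is removed, along with the response time already observed. The group is therefore selected partly on the outcome being measured. This is so even if surgery were allocated at random among patients still in response. It is stronger if better responders are the ones resected, as the DDR1 text suggests.

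At stake is a listed secondary objective. A reader would take the reported median as the durability of response to the regimen, and would compare it with trials that analyse all responders.

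The restriction may also be uneven. Section 6.4 groups resection with radiofrequency, cryoablation and radiation therapy, but the objective mentions only operated patients and does not define the term.

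**Working it through.** **Plan's own figure.** There is none to reproduce: the protocol states no expected duration of response, share operated on or time to surgery. All numbers below are assumptions chosen to show direction and range.

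**Direction.** Let T be the time from response to progression or death, and S the time from response to surgery. Responders not operated on before progression have T < S, so their durations have density proportional to f(t)·P(S > t) when T and S are independent. P(S > t) never rises with t, so long durations are weighted down and the retained durations are stochastically shorter than those of all responders. If surgery favours good prognosis, the effect is larger.

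**Closed-form check.** Assume exponential T with a true median of 9.0 months, and surgery at month t in a fraction f of those still responding.

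- S(t) = 2^(−t/9)
- Share of all responders operated on = f·S(t)
- After exclusion, S*(t) = S(t)(1−f) / (1 − f·S(t))
- Median after exclusion = t + ln(S*(t)/0.5) × 9/ln 2

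For t = 4, S(4) = 0.735. With f = 0.2, S*(4) = 0.735 × 0.8 / (1 − 0.147) = 0.689, and the median is 4 + ln(1.378) × 12.98 = 8.17.

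| Surgery at month | f among those still responding | Share of responders operated on | Median after exclusion | Shortfall |
|---|---|---|---|---|
| 4 | 5% | 4% | 8.82 | 2% |
| 4 | 10% | 7% | 8.62 | 4% |
| 4 | 20% | 15% | 8.17 | 9% |
| 4 | 40% | 29% | 6.89 | 23% |
| 1.5 | 20% | 18% | 8.65 | 4% |
| 1.5 | 40% | 36% | 8.09 | 10% |

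Both the share operated on and the timing matter.

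**Simulation with spread-out surgery.** There were 400,000 responders per scenario, with surgery uniform over months 1 to 5 after response onset. That window fits the combination phase: section 6.4 says "12 cycles have to be delivered consecutively or not", and 12 × 14 days = 168 days, about 5.5 months. Time was treated as continuous, although section 5.1 notes that "CT-Scans will be performed every 8 weeks". In the linked case, hazards vary between patients (gamma, shape 2, mean 1) and better-prognosis responders are operated on more often. The true median is 9 months, to within simulation error.

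| Responders operated on | Exclusion, surgery unrelated to prognosis | Censoring at surgery | Exclusion, surgery linked to good prognosis | Censoring at surgery |
|---|---|---|---|---|
| 5% | 8.82 (−2%) | 9.00 | 8.66 (−4%) | 8.90 |
| 10% | 8.67 (−4%) | 9.05 | 8.32 (−7%) | 8.82 |
| 20% | 8.16 (−9%) | 9.02 | 7.52 (−16%) | 8.58 |
| 30% | 7.52 (−17%) | 9.03 | 6.61 (−27%) | 8.39 |
| 40% | 6.59 (−27%) | 8.99 | 5.38 (−40%) | 8.00 |

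With true medians of 6, 9 and 12 months together, the shortfall from exclusion ran from 1% to 48% and was never upward. Censoring at surgery recovered the true median when surgery was unrelated to prognosis. In the linked case it was somewhat low, but closer than exclusion in every row.

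**The case against.** **It is only an objective line, not an analysis rule.** Partly stands. Nothing says in operational terms that operated responders are deleted rather than censored, and the endpoint is otherwise undefined. But exclusion is the natural reading, and no other section corrects it.

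**The figure is right for the group it names.** Also partly stands. It would describe non-operated patients, and separating drug-induced response from disease status after resection is a legitimate aim. That aim is met by stopping the clock at the procedure. The non-operated group cannot be identified when response starts, so its figure does not answer how long responses last.

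**The size may be small.** Stands. At 5–10% operated on, or with early surgery, the shortfall is about 2–10%. Sampling error could exceed it. Assuming 35 responders and no censoring, the standard error of a 9-month exponential median is √(0.25/35) / (0.5 × ln 2/9) = 0.0845/0.0385 = 2.2 months, a 95% half-width of about 4 months. Noise limits the practical weight but does not remove the bias.

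**Stronger readings a reader might infer.** The documents do not support these:

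- *That the regimen is meant to convert patients to resection, so its success would shorten its own reported duration.* Conversion is background in section 1 and resectability is one secondary objective. Entry requires unresectable disease, hepatectomy is described as not planned at the outset, and the primary endpoint is 48-week disease control.
- *That surgery requires response for some months.* Section 6.4 asks only that disease becomes accessible, with a recommended 4-week interval after the last chemotherapy, and it allows procedures before the 12 cycles are complete.
- *That ablated or irradiated patients certainly stay in.* This is likely on a literal reading, but the term for operated patients is undefined.

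**Conclusion.** The point holds as a selection problem in a descriptive secondary objective. Taken literally, the restriction understates duration of response for responders as a whole. The direction could reverse if operated responders would otherwise have progressed sooner, which the documents do not suggest, or if operations after progression also count, which they do not settle.

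The size cannot be derived from the protocol. With an assumed true median of 9 months it runs from about 2–10% (5–10% of responders operated on, or early surgery) to about 25% or more at the upper end. With surgery spread over months 1 to 5, 30–40% operated on gives 17–27% without a link to prognosis and 27–40% with one.

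No test, threshold or decision depends on this item. The primary endpoint is unaffected, PFS and OS carry no surgery exclusion, response rate is taken over all included patients, and resection rates are reported separately. The change is worth making because it is cheap and the literal text gives a misleading figure.

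**What to change.** In section 2.1.2 and the synopsis, change the objective to duration of response in all responders (CR or PR), and add the definition to 2.2.2 and 10.3:

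- Start at first documented response; event is progression or death; estimate by Kaplan-Meier.
- Censor at the last tumour assessment before the first resection or loco-regional procedure, with the same rule for surgery, ablation and radiotherapy of metastases. Censor responders with no event and no procedure at their last tumour assessment.
- Add a sensitivity estimate that ignores the procedure, because censoring there may be informative.
- Label any figure for the non-operated subset as descriptive, and do not present it as the duration of response.

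The cost is rewording and one extra estimate. No new assessments are needed; the sponsor should confirm that the date of each procedure is recorded, including ablation and radiotherapy. Some informative censoring will remain: in the linked scenarios above, censoring gave medians of 8.9 down to 8.0 against 9.0. The sensitivity estimate also depends on scans after the procedure, and the three-monthly follow-up in section 5.5 lists no imaging, so its completeness should be reported.

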## 2.2 Endpoints

### 2.2.1 Primary endpoint

**Phase I:** Adverse events as graded using the common toxicity criteria from the NCI-CTCAE V5 and incidence rates of DLT at each dose level during the 3 first cycles of combination therapy,

**Dose-limiting toxicities** (DLT) are defined as the occurrence of one or more of the following drug-related toxicities during the three first cycles of treatment:

#### Non-Hematologic DLT:

- Missing > 7 days daily doses of regorafenib due to drug-related toxicity (scheduled treatment pause of regorafenib will not be counted),
- Grade  $\geq 3$  (NCI-CTCAE V5) non-hematologic toxicity, except:
  - Grade 3 nausea, vomiting, diarrhea and grade 2 alopecia
  - any untreated HFSR that can be adequately controlled with medical intervention,
  - Grade  $\geq 3$  lipase elevation without signs of pancreatitis,

- Grade ≥ 2 posterior reversible encephalopathy syndrome (PRES),
- Grade ≥ 2 retinopathy,
- Liver-specific DLTs are:
  - Drug-related gr. 3-4 bilirubin increase
  - Drug-related gr. 3-4 AST and/or ALT increase
  - Drug-related AST and/or ALT increase > 3 x ULN and associated with concurrent bilirubin increase(> 2 x ULN)

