**Prophylactic G-CSF will be systematically given after each course from Day-7 to Day 12.**

**REGORAFENIB** will be given orally at a dose of 80 to 160 mg, as per dose-level, once daily on days 4 to 10 of each cycle

Tumor assessments (computed tomography (CT) or magnetic resonance imaging (MRI)) of the chest, abdomen, pelvis (if patient allergic to iodine contrast agents) will be performed at the baseline, every 8 weeks thereafter.

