## Phase I

DLT monitoring must be performed during the first three cycles of treatment. Patients will be treated until disease progression.

In case of patient withdrawal before completing the entire third cycle for reasons other than DLT, a new patient will be included at this dose level.

The phase I part of this study will be designed as a standard 3+3 design for dose escalation/de-escalation and 3 to 6 patients will be enrolled in each cohort sequentially, depending on occurrence of dose limiting toxicities (Figure 1).

A standard 3 + 3 design will be followed in the dose escalation part of study.

Three dose levels for Irinotecan/Regorafenib (IRI 150/REGO 120, IRI 180/REGO 120, IRI 180/REGO 160) are planned as well as a -1 level (IRI 150/REGO 80) to be opened in case of maximum tolerated dose (MTD) was reached at level 1 (Table 1).

Table 1 :

Steps	Dose Levels	Number of patients
DL-1	IRI 150/REGO 80	0-6
DL1	IRI 150/REGO 120	3-6
DL2	IRI 180/REGO 120	3-6
DL3	IRI 180/REGO 160	3-6

At each dose level, three patients will be included. Three additional patients will be enrolled at the same dose level if one dose limiting toxicity (DLT) is observed in the first three patients of this dose level (Figure 1).

Figure 1 :

[figure not shown]

Table 2 : Dose escalation rules

Outcome (# DLT / # Patients)	Action
0 DLT out of the first 3 patients	Include 3 patients at the next dose level
1 DLT out of 3 patients	Include 3 additional patients at the same dose level.
$\geq 2$ DLT out of 3 patients	Stop dose escalation. Include 3 additional patients at the previous dose level (unless 6 subjects were already treated).
$\geq 2$ DLT out of 6 patients	Stop dose escalation. Include 3 additional patients at the previous dose level (unless 6 patients were already treated).

The MTD is defined as the dose at which at least two out of three to six patients experienced a DLT during the first three cycles of treatment.

Dose escalation will be stopped if MTD is reached or the last dose level (IRI 180/REGO 160) is reached (MTD not reached).

The recommended phase II dose (RP2D) is defined as the dose closest to the MTD at which a DLT is observed in 0/3 or 1/6 patients.

Should any patient discontinue the study prior to completing the entire (3 cycles) for reasons other than a DLT then a replacement patient will be added at that dose level.

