**With this treatment, prophylactic G-CSF will be systematically given after each course from Day 7 to Day 12.**

### **REGORAFENIB administration (Phase I and II):**

-On days 4–10 of each cycle, all patients will receive Regorafenib orally once daily depending on dose levels for phase I and RPD2 for phase 2.

- 1 cycle = 15 days

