## 6.6 Dose modification and Dose delay

### FOLFIRINOX

**Table 4 : Hematological criteria for dose modification/interruption of Folfirinox**

CBC on D15	CYCLE DELAY	DOSE REDUCTION			
		Irinotecan (CPT-11)	Oxaliplatin (L-OHP)	LV5FU**	
PNN $\geq 1.5 \times 10^9/l$ and plat. $\geq 100 \times 10^9/l$	No cycle delay	no dose reduction			
PNN $< 1.5 \times 10^9/l$	Treatment delayed until PNN $\geq 1.5 \times 10^9/l$ (until D29 if necessary).  In case of no recovery on D29, treatment stop, *	1st episode: dose reduction to 120 mg/m  2nd episode: maintain dose at 120 mg/m  3rd episode: treatment stop	1st episode: no dose reduction 2nd episode: reduce dose to 60 mg/m  3rd episode: treatment stop	1st episode: no dose reduction 2nd episode: no dose reduction 3rd episode: treatment stop	
Plat. $< 100 \times 10^9/l$	Delay treatment until recovery (plat. $\geq 100 \times 10^9/l$ ).  If no recovery on D29, treatment stop	1st episode: no dose reduction 2nd episode: reduce dose to 120 mg/m  3rd episode: treatment stop	1st episode: reduce dose to 60 mg/m  2nd episode: maintain dose at 60 mg/m  3rd episode: treatment stop	1st episode: no dose reduction 2nd episode: reduce the dose by 25% 3rd episode: treatment stop	

Measures in case of hematological toxicity during the inter-cycle interval (nadir):

 
-Febrile neutropenia* isolated
 
-Grade 4 neutropenia > 7 days
 
-Infection concomitant with grade 3-4 neutropenia
 
	
1st episode: reduce irinotecan dose to 120 mg/m^2
 
2nd episode: in addition reduce oxaliplatin dose to 60 mg/m^2
 
3rd episode: discuss further treatment reduction, maintain only LV5FU if necessary.

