**Table 5 : Dose modifications in case of digestive toxicities**

EVENTS	DOSE REDUCTION

 
-Isolated grade 3-4 diarrhea or
 
-Diarrhea + fever and/or grade 3-4 neutropenia
 
	
1st episode: reduce irinotecan to 120 mg/m^2
 
2nd episode: reduce oxaliplatin to 60 mg/m^2 and reduce 5-FU continue by 25 %
 
3rd episode: stop irinotécan

Recurrent diarrhea (>48 h) despite high doses of loperamide	No dose reduction for irinotecan, oxaliplatin and 5-FU after recovery except if grade 3-4 diarrhea, or diarrhea + fever and/or grade 3-4 neutropenia

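### Losing a full regorafenib cycle, or chemotherapy, to toxicity is not in itself a DLT, and such patients are replaced or scored DLT-free, which lowers the observed DLT rate

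*Combined protocol and SAP*

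**What the plan says.** Section 2.2.1, like the synopsis, lists as a DLT "Missing > 7 days daily doses of regorafenib due to drug-related toxicity" and adds that a "scheduled treatment pause of regorafenib will not be counted". This is the only item about treatment not given. The other items define DLTs by type and grade of toxicity. None mentions delay, omission or permanent stop of irinotecan, oxaliplatin or 5-FU. The exceptions to the grade 3 or higher non-hematologic item include "Grade 3 nausea, vomiting, diarrhea and grade 2 alopecia".

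The synopsis gives regorafenib "once daily on days 4 to 10 of each cycle" and section 6.1 agrees: "On days 4–10 of each cycle, all patients will receive Regorafenib orally once daily". The DLT window is the first three cycles.

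Section 6.6 foresees toxicity-driven loss of chemotherapy. For neutrophils below 1.5 x 10^9/l, Table 4 says "In case of no recovery on D29, treatment stop", with a matching rule for platelets below 100 x 10^9/l. For a first episode of grade 3-4 diarrhea, Table 5 says "reduce irinotecan to 120 mg/m 2"; a third episode stops irinotecan.

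Section 3.1 provides that if a patient leaves before completing three cycles "for reasons other than a DLT then a replacement patient will be added at that dose level". Section 9.1 states that stopping treatment is not the same as withdrawing from the trial. Section 3.1 defines the maximum tolerated dose (MTD) and the recommended phase II dose (RP2D) by DLT counts alone; an RP2D level must show 0/3 or 1/6.

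**The concern.** The missed-dose threshold sits exactly at one cycle's supply, so losing a complete cycle falls one dose short of it. Separately, irinotecan is one of the two escalated drugs, yet losing it to toxicity is no criterion at all. These are two distinct gaps; the second does not follow from the dose count.

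The statistical harm comes through the denominator. A patient who stops for drug-related toxicity that is not on the list has given information against the dose. Replacing that patient discards the information, and scoring the patient as DLT-free reverses it. Either way the DLT rate that drives escalation and the RP2D is biased downward.

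Such losses are foreseeable. In the doublet-plus-regorafenib study cited in section 1, drug-related events led to dose modification, interruption or discontinuation in 69% of patients, and 52% (FOLFOX) and 65% (FOLFIRI) had a chemotherapy component reduced or interrupted. Those figures concern doublets and are not limited to three cycles, so they do not give a rate for this trial.

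**Working it through.** **The plan's own figure.** The phase I maximum reproduces: 4 dose levels x 6 patients = 24 (section 10.1). The missed-dose threshold has no stated derivation to reproduce.

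**Dose count.** Days 4 to 10 give 10 - 4 + 1 = 7 doses per cycle, and 3 x 7 = 21 in the window. More than 7 means at least 8, and 8/21 = 38%. One full cycle is 7/21 = 33%.

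| Situation | Doses missed | More than 7? |
|---|---|---|
| Most that can be missed in one cycle (per-cycle reading) | 7 | never |
| One full cycle lost (cumulative) | 7 | no |
| One full cycle plus one further dose (cumulative) | 8 | yes |
| All treatment stopped after cycle 2 | 7 | no |
| All treatment stopped after cycle 1 (cumulative) | 14 | yes |
| Chemotherapy stopped, regorafenib continued | 0 | no |

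**Blood counts.** Take neutrophils of 1.2 or platelets of 80 x 10^9/l after cycle 2, unrecovered on D29. Table 4 stops treatment. Neither count meets a hematologic DLT: those need grade 4 neutropenia for more than 3 days, febrile neutropenia, platelets below 25,000/mm3, or below 50,000/mm3 with bleeding. Table 9 does not interrupt regorafenib at these counts, so 0 doses are missed if it continues and 7 if it stops as well. Neither exceeds 7.

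**Diarrhea.** Suppose grade 3 diarrhea recurs in the window. Table 5 brings irinotecan below both tested levels (150 and 180 mg/m2) after the first episode. If the diarrhea is attributed to regorafenib, Table 8 interrupts that drug too. Three episodes must then cost 8 doses in all (8/3 = 2.7 each) to meet the cumulative reading. Below that, no DLT is recorded.

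**Effect on the 3+3 rule.** A level passes with 0/3, or with 1/3 followed by 0/3:

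P(pass) = (1 - r)^3 + 3r(1 - r)^2 x (1 - r)^3

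The documents give no rates for the triplet, so these are assumed: p = 0.20 for a listed DLT and q = 0.05 to 0.15 for an unlisted toxicity stop in the window. The two are treated as mutually exclusive and patients as independent. The rate r that the rule sees is p + q if all count, p/(1 - q) if the stops are replaced, and p if they are scored DLT-free.

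| q | All count: r, P(pass) | Replaced: r, P(pass) | DLT-free: r, P(pass) |
|---|---|---|---|
| 0.05 | 0.25, 0.600 | 0.211, 0.686 | 0.20, 0.709 |
| 0.10 | 0.30, 0.494 | 0.222, 0.660 | 0.20, 0.709 |
| 0.15 | 0.35, 0.396 | 0.235, 0.632 | 0.20, 0.709 |

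For q = 0.15, all counted: 0.65^3 = 0.275; 3 x 0.35 x 0.65^5 = 0.122; sum 0.396 before rounding of the terms. Replaced: r = 0.20/0.85 = 0.235, giving 0.447 + 0.185 = 0.632.

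**The case against.** Read cumulatively, more than 7 of 21 is a coherent threshold, and nothing in the documents obliges the sponsor to count one lost cycle. Where to set a clinical DLT threshold is a matter on which experts differ. That stands, and no threshold is proposed here.

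Several stronger readings are tempting, and the documents do not support them:

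- A reader might infer that a lost cycle or a chemotherapy stop can never be a DLT. It is one whenever its cause meets another criterion: most grade 3 or higher non-hematologic toxicity, the liver events, febrile neutropenia, prolonged grade 4 neutropenia, the platelet and bleeding items.
- A reader might infer that the patient with low counts loses exactly 7 regorafenib doses and is then replaced. Table 9 points to no regorafenib interruption, and section 9.1 suggests that the patient may stay in the count as DLT-free. The plan settles neither.
- A reader might infer that repeated grade 3 diarrhea necessarily scores as tolerance. Under Table 8, enough missed doses could still make it a DLT, and grade 4 diarrhea is not exempt.
- A reader might infer that phase II will be run at an undeliverable dose. Under section 3.1 the project team can stop or modify escalation after seeing all relevant safety findings, and the committee in section 11.2.7 advises before phase II. All graded adverse events also belong to the phase I primary endpoint.

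These safeguards are real, but they are discretionary and come with no criterion for lost treatment. The committee's end-of-phase-I review itself refers to the number of DLTs. They do not repair the DLT count.

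**Conclusion.** The point holds in this form: losing one full cycle of regorafenib, or losing chemotherapy to drug-related toxicity, is not in itself a DLT unless another listed criterion is met. Patients who stop in the window for unlisted drug-related toxicity are either replaced or counted as DLT-free, depending on how sections 3.1 and 9.1 are read together. Both routes bias the observed DLT rate down.

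On the assumed rates, the chance that a level passes rises by 9 percentage points (replaced) or 11 (DLT-free) with 5% unlisted stops, and by 24 or 31 points with 15%. The direction of the bias does not depend on these rates; its size does. The figures describe passing one level, not the choice of RP2D, and the comparison takes as reference a count that includes the unlisted stops.

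This should be fixed. It falls short of a defect that invalidates phase I, because other criteria catch many toxicities and the oversight bodies can act.

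**What to change.** In section 3.1, at both statements of the replacement rule, restrict replacement to patients who leave the DLT window for reasons unrelated to drug toxicity. Keep patients who leave or stop study treatment in the window for drug-related toxicity in the denominator, without replacement. State in advance how they are scored, and report the DLT rate at each level a second time with these patients counted as events. This changes how patients are counted, not how they are treated.

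Reconcile the synopsis DLT list, sections 2.2.1, 3.1 and 9.1, and Tables 4, 5, 8 and 9 of section 6.6 on three questions:

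1. Is the missed-dose item per cycle, or cumulative over the 21 doses?
2. Do doses not given because a cycle is delayed or omitted count as missed?
3. How is toxicity-driven loss of chemotherapy scored?

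The clinical thresholds are for the sponsor to choose.

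The cost is low: adverse-event records already include the action taken, and drug accountability is already planned (section 5.3). The downsides are that escalation may stop one level earlier, and that changing the phase I endpoint may need a substantial modification under section 13.6.
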